 - Corrected calcium value \leq 1.1 x ULN
 - Total bilirubin \leq 1.5 x ULN (upper limit of normal) except subject with documented Gilbert's syndrome (\leq 5 x ULN) or liver metastasis, who must have a baseline total bilirubin \leq 3.0 mg/dL
 - AST and ALT \leq 3 x ULN, unless associated with hepatobiliary metastases, in that case \leq 5 x ULN
 - ALP \leq 2.5 x ULN or \leq 5.0 x ULN for patients with bone metastases
 - Gamma-glutamyltransferase \leq 2.5 x ULN
 - Albumin \geq 2.5 g/dL
 - Phosphate \leq 1.1 x ULN
 - Prothrombin time (PT) and/or prothrombin time international normalized ratio (PT-INR) and/or activated partial thromboplastin time (APTT) \leq 1.3 x ULN
 - Serum creatinine \leq 1.5 x ULN or creatinine clearance \geq 50 mL/min on the basis of the Cockcroft–Gault glomerular filtration rate estimation:
$$\frac{(140 - \text{age}) \times (\text{weight in kg}) \times (0.85 \text{ if female, 1.00 if male})}{72 \times (\text{serum creatinine in mg/dL})}$$

- Patients with “treated and stable” brain lesions for a duration of > 4 weeks may be enrolled.
- Female subjects of childbearing potential should have a negative urine or serum pregnancy test within 72 hours prior to receiving the first dose of study medication and agree to use effective contraception. If the urine test is positive or cannot be confirmed as negative, a serum pregnancy test will be required. Note: Abstinence is acceptable if this is the usual lifestyle and preferred contraception for the subject.

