9.2.7 Prophylaxis for skin toxicity and alopecia

Guidelines for prophylaxis are detailed in Appendix A.

9.3 Dose-limiting toxicity during Phase 1

The following AEs or laboratory abnormalities, graded according to NCI-CTCAE version 4, are considered to be DLTs when occurring during the DLT evaluation period (Day 1 to Day 28 of Cycle 1, plus the assessments prior to drug administration on Cycle 2, Day 1 and the Investigator feels are possibly, probably, or definitely related to Debio 1347 excluding those that are clearly and incontrovertibly due to disease progression or extraneous causes.:

- Febrile neutropenia (ANC < 1.0 X 10⁹/L and fever ≥ 38.2°C [101° F])

- Grade 3 or higher neutropenia with infection.
- Grade 4 neutropenia persisting for more than 7 days.
- Grade 4 thrombocytopenia persisting for more than 7 days or Grade 3 thrombocytopenia requiring platelet transfusion.
- Grade 3 diarrhea, constipation, nausea, vomiting or skin toxicity that lasts longer than 72 hours despite optimal symptomatic therapy.
- Any Grade 4 diarrhea, constipation, nausea, vomiting or skin toxicity.
- Grade 3 or higher liver function tests (ALT, AST, γ GPT) and ALP unless as clarified below
- Grade 3 or higher non-hematologic toxicity including Hy's law: AST and/or ALT $> 3 \times$ ULN and bilirubin $> 2 \times$ ULN, and without initial findings of cholestasis (serum alkaline phosphatase (ALP) activity $< 2 \times$ ULN) and no other reason that could explain the combination of increased transaminases and serum total bilirubin, such as viral hepatitis A, B, or C, preexisting or acute liver disease (including preexisting liver metastases), or another drug capable of causing the observed injury.
- The following non-hematologic AEs are not considered DLTs:
 - a. Grade 3 electrolyte abnormalities lasting < 24 to 72 hours, is not clinically complicated, and resolves spontaneously or responds to conventional medical interventions; and \geq Grade 3 amylase or lipase that is not associated with symptoms or clinical manifestations of pancreatitis.
 - b. Grade 3 or higher of ALP clearly related to bone metastases evolution. The relationship should be discussed with the study Medical Monitor on a case by case basis.
- Hyperphosphataemia:
 - a. Serum Pi > 7.0 mg/dL for > 7 consecutive days despite phosphorus lowering therapy for at least 14 days.
 - b. Serum Pi > 9.0 mg/dL, despite phosphorus lowering therapy for at least 14 days.
 - c. Serum Pi > 10.0 mg/dL.

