9.4 Dose Modifications or Scheduling Delays

- This study will use the NCI Common Toxicity Criteria (CTC) AE version 4.0 for toxicity.
- Study treatment will be temporarily or permanently discontinued due to the occurrence of AEs as specified in Table 1 below, for both the phase 1 and 2 portions of this study.
- Additionally, non-treatment related or unexpected toxicities may require interruption of therapy at the discretion of the Investigator.

- Failure to recover to the specified levels following temporary discontinuation within 7 days in the phase 1b portion and 14 days in the phase 2 portion will result in permanent treatment discontinuation. The treating Investigator and the PI will discuss the case of any patient whose treatment has been delayed for more than 7 or 14 days, respectively, who they think may benefit from continued treatment, prior to resuming treatment.
- In addition, if Grade 2 or higher toxicity occurs, treatment may be temporarily discontinued at the discretion of the Investigator. The patients may resume at the same dose level when toxicity has resolved to Grade 1 or below or the baseline level if resolution is achieved within 7 days in the phase 1b part and 14 days in the phase 2 part.
- In the event the patient requires temporary treatment discontinuation, the Investigator may choose to increase the frequency of the assessments performed to weekly collections until resolution.
- Only in the phase 2 portion, one dose reduction can be undertaken except for dose level -1 (60mg). Patients resuming treatment following a temporary discontinuation can do so at their original dose level or at one lower dose level.
- Patients experiencing a DLT during the DLT period may continue treatment after dose adjustments if there is a potential benefit from treatment after discussion with the PI
- Patients will be permanently discontinued if reduction beyond <60mg/day is necessary in both phase 1 and phase 2 portions of the study
- Reduced doses may not be re-escalated.
- If a patient discontinues Debio 1347 purely due to toxicity, they can stay on study and continue to receive fulvestrant. The patient will be captured as coming off of Debio 1347 due to toxicity and report TTF.

Table 1: Dose Modifications and Delays during Phase 1 and Phase 2

Adverse Event	Grade	Action	
		Phase I part: DLT evaluation period only	Phase I part: non-DLT evaluation period Phase 2 portion

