Febrile neutropenia, Neutropenia with infection	4	Permanent discontinuation	Permanent discontinuation
	3	Permanent discontinuation	Temporary discontinuation until recovery to Grade 0
Neutropenia	3, 4	Temporary discontinuation until recovery to Grade 2	Temporary discontinuation until recovery to Grade 2
Thrombocytopenia	4	Permanent discontinuation	Temporary discontinuation until recovery to Grade 1
	3	Temporary discontinuation until recovery to Grade 1 Permanent discontinuation if a platelet	If a platelet transfusion is required, temporary

Adverse Event	Grade	Action	
		transfusion is required	discontinuation until recovery to Grade 1
Diarrhea, constipation, nausea, vomiting	3,4	Permanent discontinuation, if not manageable by optimal symptomatic therapy	Temporary discontinuation until recovery to Grade 2, or baseline
Skin toxicity (See additional guidelines in 9.4.1)	3,4	Permanent discontinuation, if not manageable despite prophylaxis and optimal symptomatic therapy	Temporary discontinuation until recovery to Grade 2, or baseline
Hyperphosphataemia		Please use the treatment guidelines per 9.4.2	Please use the treatment guidelines per 9.4.3
Hypertension	4	Permanent discontinuation	Permanent discontinuation
	3	Permanent discontinuation	If uncontrolled, temporary discontinuation until control is achieved
Hepatotoxicity (AST, ALT, ALP, γ GTP increased)	4	Permanent discontinuation	Permanent discontinuation
	3	Temporary discontinuation, until recovery to Grade 2	Temporary discontinuation, until recovery to Grade 2
Other non-haemotoxicity (except for transient electrolyte abnormalities)	4	Permanent discontinuation	Permanent discontinuation
	3	Permanent discontinuation	Temporary discontinuation until recovery to Grade 1 or baseline
Recovery from above AEs		Permanent discontinuation, if failure to recover within 7 days, otherwise treatment at same dose level. Dose reduction during the DLT has to be discussed with the PI	Permanent discontinuation, if failure to recover within 14 days, otherwise retreatment at next lowest dose level

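### Table 1 has no criterion for AST/ALT rising together with bilirubin (the Hy's law pattern), so in Phase 2 a Grade 3 event that recovers within 14 days is directed to retreatment with Debio 1347 at 60 mg

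*Combined protocol and SAP*

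**What the plan says.** Section 9.4 applies Table 1 to both phases. One column covers Phase 2 and also Phase 1 after the DLT period. Section 9.2.1 records that all Phase 1 patients were off study at the amendment, so the practical reach now is Phase 2, at 80 mg daily (section 9.1) in up to 43 patients.

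The liver row of Table 1 is "Hepatotoxicity (AST, ALT, ALP, γ GTP increased"). Bilirubin is not among its analytes. In the Phase 2 column, Grade 4 is a permanent stop and Grade 3 is a hold until Grade 2. Other non-haematological toxicity has its own row: Grade 4 is a permanent stop, and Grade 3 is a hold until Grade 1 or baseline. Both rows then feed the recovery row: "Permanent discontinuation, if failure to recover within 14 days, otherwise retreatment at next lowest dose level".

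The combined pattern appears only in section 9.3, in the list of Phase 1 DLTs, where it also requires absence of cholestasis and "no other reason that could explain the combination of increased transaminases and serum total bilirubin". It counts only in Cycle 1 and the assessments before dosing on Cycle 2 Day 1, and a patient with a DLT may continue after adjustment.

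Section 11.1 lists AST, ALT, alkaline phosphatase and bilirubin rises as expected effects of Debio 1347. Section 11.2 lists ALT, AST and ALP rises for fulvestrant.

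**The concern.** A transaminase rise with a bilirubin rise, without cholestasis or another explanation, points to possible severe drug-induced liver injury. The protocol recognises this, since it wrote the definition into section 9.3. In Phase 2, where patients are treated until progression, Table 1 treats each value as a separate graded event and directs retreatment once it improves.

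A patient with a suspected serious liver reaction could therefore be re-exposed by following the table as written. The documents give some reason to care about this drug: a Grade 3 bilirubin increase was among the DLTs at 110 mg (section 3.3.4), liver effects were seen in the animal studies (section 3.3.3), and the bile salt export pump is inhibited in vitro (section 9.1.2).

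**Working it through.** The plan gives no figure to reproduce. The check traces the rules for a Phase 2 patient on 80 mg with Grade 3 AST/ALT and bilirubin above 2xULN.

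1. **Bilirubin below Grade 3.** The liver row holds Debio 1347 until the enzymes reach Grade 2 and sets no bilirubin recovery condition. Recovery within 14 days leads to retreatment one level lower.
2. **Bilirubin Grade 3.** The row for other non-haematological toxicity also applies, so bilirubin must return to Grade 1 or baseline. Recovery within 14 days again leads to retreatment one level lower.
3. **Whole event read as other non-haematological toxicity.** Section 9.3 groups Hy's law with Grade 3 or higher non-haematological toxicity, so this reading is open. The hold lasts to Grade 1 or baseline, and the recovery row then directs retreatment.
4. **Any value Grade 4.** Permanent stop.
5. **No recovery within 14 days.** Permanent stop, subject to the discussion with the principal investigator allowed in section 9.4.
6. **Patient already at 60 mg.** No lower level exists, and section 9.4 stops a patient who needs a reduction below it.

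In cases 1 to 3 no step stops the drug because the two abnormalities occur together. The gap is therefore a first event at 80 mg, below Grade 4, that recovers in time.

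**Size of the dose step.** 60/80 = 0.75, a reduction of 25%. Section 3.3.4 describes exposure as roughly dose-proportional from 10 to 150 mg, so exposure would also fall by only about a quarter.

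**Entry limits in section 6.2 against the section 9.3 thresholds.** These show why a new row needs a baseline rule.

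- Gilbert's syndrome: bilirubin up to 5xULN; 5/2 = 2.5 times the threshold.
- Liver metastases, enzymes: AST/ALT up to 5xULN; 5/3 = 1.67 times.
- Liver metastases, bilirubin ("or liver metastasis, who must have a baseline total bilirubin" no higher than 3.0 mg/dL): assuming a ULN of 1.0 to 1.2 mg/dL, which the documents do not state, this is 3.0 to 2.5xULN, or 1.5 to 1.25 times the threshold.
- Bone metastases: ALP up to 5xULN; 5/2 = 2.5 times the ALP limit. The general ALP entry limit of 2.5xULN is also above it, 2.5/2 = 1.25 times.

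Without a baseline rule the enzyme and bilirubin limits could be met before the first dose, and raised bone ALP could keep the row from ever applying.

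**The case against.** The strongest reply is that retreatment is not compelled. Section 10.1.3 ends treatment for unacceptable toxicity or in the patient's interests as the investigator judges them, and section 13 makes unacceptable adverse experiences a mandatory reason for discontinuation. A competent investigator would probably stop. That stands, and a reader who inferred that the protocol forces the patient back on drug would be wrong. But neither provision defines this pattern, while Table 1 directs retreatment.

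The clinical record is also reassuring as far as it goes. Among 57 patients in the dose-escalation study, the only bilirubin DLT listed was at 110 mg, above the Phase 2 dose, and no combined event is described.

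Three stronger readings are tempting and not supported.

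- **Retreatment at full dose.** A section 9.4 bullet says "Patients resuming treatment following a temporary discontinuation can do so at their original dose level or at one lower dose level". Section 9.4 sends the listed events to Table 1, which specifies the lower level, so the bullet can be read as covering other holds. At most this is a separate inconsistency of wording.
- **Too little monitoring to show recovery.** During a hold "the Investigator may choose to increase the frequency of the assessments performed to weekly collections until resolution", and from Cycle 3 chemistry is scheduled only on Day 1 of each 28-day cycle. But if no test is drawn within 14 days, recovery is not shown and the rule points to stopping, not to re-exposure.
- **No mandatory action when both values are below Grade 3.** Whether the pattern can occur there depends on CTCAE cut-offs that the documents do not give. If it can, the cover is discretionary ("if Grade 2 or higher toxicity occurs, treatment may be temporarily discontinued at the discretion of the Investigator"), but resumption at the same dose then requires return to Grade 1 or below, or to baseline, within 14 days.

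**Conclusion.** The gap is real and narrow. In Phase 2 no explicit rule stops Debio 1347 for AST/ALT and bilirubin rising together. A recovered Grade 3 event at 80 mg is directed to 60 mg, 75% of the dose and about 75% of the exposure. This holds whichever Table 1 row is used; the choice of row changes only the recovery level required. Protection beyond that rests on investigator judgement.

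The conclusion comes from the text of sections 9.3 and 9.4. The exposure figure assumes the approximate dose-proportionality reported in section 3.3.4. No rate for the combined pattern is available, so the expected number of affected patients among the 43 cannot be stated. This is a cheap safety improvement; the primary endpoint and the two-stage design are unaffected.

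**What to change.** Add a row to Table 1, in the column for Phase 2 and the non-DLT period, using the section 9.3 criterion: AST and/or ALT above 3xULN with total bilirubin above 2xULN, ALP below 2xULN, and no cause other than study treatment.

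- **Action.** Hold Debio 1347 while the cause is checked. Recheck AST, ALT, ALP and bilirubin within 7 days; section 9.4.3 already sets that interval for phosphate.
- **No non-study cause found.** Permanently discontinue Debio 1347.
- **Non-study cause found.** The existing Table 1 rules apply, with both enzymes and bilirubin back to Grade 1 or baseline before restart.
- **Existing stops.** Grade 4 events and failure to recover within 14 days still lead to permanent discontinuation.
- **Footnote.** Give a baseline-relative criterion, with limits set by the sponsor, for patients admitted under section 6.2 with raised bilirubin, AST/ALT or ALP (Gilbert's syndrome, liver or bone metastases). Section 9.3 counts pre-existing liver metastases as an alternative cause, so the footnote should say how they are handled.

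No new fulvestrant rule is needed. Section 9.4 already provides: "If a patient discontinues Debio 1347 purely due to toxicity, they can stay on study and continue to receive fulvestrant".

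The cost is one row and one footnote. Total bilirubin, AST, ALT and ALP are already in the chemistry panel (section 10.1, footnote d). The downside is that a few patients stop Debio 1347 who could now be retreated, plus a few repeat blood draws.

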9.4.1 Skin Toxicity, nail toxicity and alopecia

Patients will be referred to [name] (Dermatology) for management of alopecia, skin, nail toxicity and stomatitis as needed. Of note, patients will be allowed to receive prophylaxis for skin toxicity and alopecia per section 9.2.7 and Appendix A. Specific treatment guidelines are also detailed in Appendix A.

9.4.2 Hyperphosphatemia (Phase I)

1. Initial Modifications on Treatment:

Serum phosphorus level	
5.5 – 6.9 mg/dL	
 1. Continue Debio 1347 2. Continue (or increase) sevelamer powder 2400mg TID 3. Add Fosrenol 1g TID 4. Recheck within 7 days

≥ 7 mg/dL	
 1. Hold Debio 1347 2. Continue (or increase) sevelamer powder 2400mg TID 3. Add Fosrenol 1g TID 4. check within 7 days -> resume if Ph < 5.5 and recheck within 7 days of resumption
----------------	---

*If sevelamer is not available or tolerable, alternate phosphate reducing agents or preparations can be utilized.

2. Second Modification on Treatment

Serum phosphorus level	
5.5 – 6.5 mg/dL	
 1. Cont Debio 1347 2. Cont sevelamer powder to 2400mg TID increase Fosrenol to 1.5mg TID 3. recheck within 7 days
6.6-6.9mg/dL	
 1. Cont Debio 1347 2. Cont sevelamer powder to 2400mg TID 3. Cont Fosrenol 1g TID 4. add acetazolamide 250mg BID 5. recheck within 7 days
≥ 7 mg/dL	
 1. Hold Debio 1347 – consider dose reduction 2. Cont sevelamer powder to 2400mg TID 3. increase Fosrenol to 1.5g TID 4. add acetazolamide 250mg BID 5. check within 7 days -> resume if Ph < 5.5

*If sevelamer is not available or tolerable, alternate phosphate reducing agents or preparations can be utilized.

3. Subsequent Modifications:

Serum phosphorus level	
> 5.5 mg/dL-6.9mg/dL	
 1. If not already, maximize regimen to include: sevelamer powder to 2400mg TID fosrenol to 1.5g TID acetazolamide 250mg BID 2. If already maximized, consider dose reduction (without interrupting drug) 3. Recheck within 7 days
≥ 7 mg/dL	
 1. Hold Debio 1347 – dose reduction needed 2. Maximize regimen to include: sevelamer powder to 2400mg TID fosrenol to 1.5g TID acetazolamide 250mg BID

	3. check within 7days -> resume with dose reduction if Ph < 5.5
--	---

*If sevelamer is not available or tolerable, alternate phosphate reducing agents or preparations can be utilized.

- For patients whose phosphorous control improves after Debio 1347 dose reductions, escalation of the phosphorus regimen can be considered at the discretion of the investigator. Subsequent to any such adjustment, phosphorous level should be rechecked within 7 days.
- In case of patients with hepatic or renal impairment, it is recommended not to change hyperphosphatemia treatment even in the case of Debio 1347 dose reduction.

9.4.3 Hyperphosphatemia (Phase II)

INITIAL TREATMENT MODIFICATION	
Serum Phosphorous Level	Intervention/Modification
5.5 – 6.9 mg/dL	
 Continue treatment with Debio 1347 at current dose AND Start on sevelamer oral POWDER 1200mg three times a day (subjects may use tablets if preferred, but tends to have more gastrointestinal toxicity) Escalate to sevelamer oral POWDER or tablets 2400mg three times a day if tolerated. Reassess serum phosphorus within 7 days
≥ 7 mg/dL	
 Hold treatment with Debio1347 Start sevelamer oral POWDER or tablets 2400mg three times a day Add treatment with lanthanum carbonate (Fosrenol®) 1g three times a day Reassess serum phosphorus level within 7 days: 
 If serum phosphorus level < 5.5 mg/dL, resume Debio 1347 at same dose and recheck within 7 days of resumption
Note:	
 Sevelamer should be preferably taken in the middle of meals Lanthanum carbonate should be taken just after meals Sevelamer and lanthanum must be administered at least 2 hours after or 4 hours before Debio 1347

SECOND TREATMENT MODIFICATION	
Serum Phosphorous Level	Intervention/Modification
5.5 – 6.5 mg/dL	
 Continue treatment with Debio 1347 at a current dose AND Continue sevelamer oral POWDER or tablets 2400mg three times a day Introduce treatment with lanthanum carbonate (Fosrenol®) to 1.0g three times a day or increase to 1.5g three times a day Reassess serum phosphorus level within 7 days
6.6-6.9 mg/dL	
 Continue treatment with Debio 1347 at current dose AND Continue sevelamer oral POWDER or tablets 2400mg three times a day Introduce treatment with lanthanum carbonate (Fosrenol®) to 1.0g three times a day or increase the dose to 1.5g three times a day Add treatment with oral acetazolamide 250mg twice a day Reassess serum phosphorus level within 7 days
≥ 7 mg/dL	
 Hold treatment with Debio 1347 – consider dose reduction Continue sevelamer oral POWDER or tablets 2400mg three times a day Increase treatment with lanthanum carbonate (Fosrenol®) to 1.5g three times a day AND

	
 • Add treatment with oral acetazolamide 250mg twice a day • Reassess serum phosphorus level within 7 days: 
 ◦ If serum phosphorus level < 5.5 mg/dL, resume Debio 1347 with dose reduction
Note:	
 • Sevelamer should be preferably taken in the mid of meals • Lanthanum carbonate should be taken just after meals • Sevelamer and lanthanum must be administered at least 2 hours after or 4 hours before Debio 1347 • Acetazolamide should be preferably taken just after breakfast and dinner

SUBSEQUENT TREATMENT MODIFICATIONS

Serum Phosphorous Level	Intervention/Modification
5.5 – 6.9 mg/dL	
 • If not already done, maximize regimen to include: 
 ◦ Sevelamer oral POWDER or tablets to 2400mg three times a day ◦ Lanthanum carbonate (Fosrenol®) to 1.5g three times a day ◦ Oral acetazolamide 250mg twice a day • If regimen already maximized, consider dose reduction (without interrupting Debio 1347 assumption) • Reassess serum phosphorus level within 7 days
≥ 7 mg/dL	
 • Hold treatment with Debio1347 – dose reduction needed • Maximize regimen to include: 
 ◦ Sevelamer oral POWDER or tablets to 2400mg three times a day ◦ Lanthanum carbonate (Fosrenol®) to 1.5g three times a day ◦ Oral acetazolamide 250mg twice a day • Reassess serum phosphorus level within 7 days: 
 ◦ If serum phosphorus level < 5.5 mg/dL, resume Debio 1347 with dose reduction
Note:	
 • Sevelamer should be preferably taken in the mid of meals • Lanthanum carbonate should be taken just after meals • Sevelamer and lanthanum must be administered at least 2 hours after or 4 hours before Debio 1347 • Acetazolamide should be preferably taken just after breakfast and dinner

GENERAL RECOMMENDATIONS

- In subjects whose serum phosphorus control improves after Debio 1347 dose reduction, de-escalation of the hyperphosphatemia treatment can be considered at the discretion of the Investigator. Subsequent to any such adjustment, serum phosphorus level should be reassessed within 7 days.
- In case of subjects with hepatic or renal impairment, it is recommended not to change hyperphosphatemia treatment even in the case of Debio 1347 dose reduction.

